## 5.4 SAMPLES FOR GENETIC/GENOMIC ANALYSIS

## 5.4.1 Description of the scope of genetic/genomic analysis

Identification and prioritization of specific metastatic sites for further analysis will be made by the investigator after taking into account various factors including the prior rate of growth of disease, response to treatment and tumor fraction in the available sample. DNA and RNA will be extracted from tumor samples and germ line DNA and RNA will be extracted from PBMCs from whole blood for molecular genetic testing using Pax-gene as specified in investigator's companion protocol, 10-C-0066.

# 5.4.2 Description of how privacy and confidentiality of medical information/biological specimens will be maximized

- As part of study efforts to provide confidentiality of participant information, this study will obtain a Certificate of Confidentiality which helps to protect personally identifiable research information. The Certificate of Confidentiality allows investigators on this trial to refuse to disclose identifying information related to the research participants, should such disclosure have adverse consequences for participants or damage their financial standing, employability, insurability or reputation. The informed consent includes the appropriate coverage and restrictions of the Certificate of Confidentiality.
- Tissue and blood samples collected will be coded. DNA, RNA and protein isolated from these tissues and cell lines and xenografts generated will all be similarly coded. Only personnel involved in this study will have access to both the code and the name of the participant as specified in investigator's companion protocol, 10C0066.
- To help protect the privacy, investigators will obtain a Certificate of Confidentiality from the National Institute of Health. With this certificate, investigators cannot be forced to disclose information that may identify the participant or immediate family members, even by a court subpoena, in any federal, state, or local civil, criminal administrative, legislative or other proceedings. The researchers will use this Certificate of Confidentiality to resist any demands for information that would identify the participant or immediate family members. However, the Certificate cannot be used to resist a demand for information from personnel of the United States Government that is used for auditing or evaluation of federally funded projects or for information that must be disclosed in order to meet the requirements of the Food and Drug Administration (FDA).
- To facilitate genetic research, and for the purpose of publication of research work, data from genomic and proteomic studies may be deposited in appropriate public databases. Coded data will be deposited in a manner that the participant's identity cannot be traced.

## **5.4.3** Management of Results

Subjects will be contacted if a clinically actionable gene variant is discovered. Clinically actionable findings for the purpose of this study are defined as disorders appearing in the American College of Medical Genetics and Genomics recommendations for the return of incidental findings that is current at the time of primary analysis.

Subjects will be contacted at this time with a request to provide a blood sample to be sent to a CLIA certified laboratory. If the research findings are verified in the CLIA certified lab, the subject will be offered the opportunity to come to NIH (at our expense) to have genetic education and counseling to explain this result. If the subject does not want to come to NIH, a referral to a local genetic healthcare provider will be provided (at their expense).

This is the only time during the course of the study that incidental findings will be returned. No interrogations regarding clinically actionable findings will be made after the primary analysis.

Version Date: 04/16/2025

## **5.4.4** Genetic Counseling

The costs of CLIA testing will be paid for by the Center for Cancer Research, the Branch, or the Principal Investigator. If the health history, family history, or tumor diagnosis from the Laboratory of Pathology at the NIH Clinical Center suggests that the participant might benefit from genetic testing, we will discuss this with him/her.

## 6 DATA COLLECTION AND EVALUATION

#### 6.1 DATA COLLECTION

The PI will be responsible for overseeing entry of data a 21 CFR Part 11-compliant data capture system provided by the NCI CCR and ensuring data accuracy, consistency and timeliness. The principal investigator, associate investigators/research nurses and/or a contracted data manager will assist with the data management efforts. Primary and final analyzed data will have identifiers so that research data can be attributed to an individual human subject participant.

All adverse events, including clinically significant abnormal findings on laboratory evaluations, regardless of severity, will be followed until return to baseline or stabilization of event.

Document AEs from the first study intervention, Study Day 1, through the end of treatment. After 30 days, only adverse events which are serious and related to the study intervention need to be recorded.

An abnormal laboratory value will be recorded in the database as an AE **only** if the laboratory abnormality is characterized by any of the following:

- Results in discontinuation from the study
- Is associated with clinical signs or symptoms
- Requires treatment or any other therapeutic intervention
- Is associated with death or another serious adverse event, including hospitalization.
- Is judged by the Investigator to be of significant clinical impact
- If any abnormal laboratory result is considered clinically significant, the investigator will provide details about the action taken with respect to the test drug and about the participant's outcome.

**End of study procedures:** Data will be stored according to HHS, FDA regulations, and NIH Intramural Records Retention Schedule as applicable.

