A total of 48 phase I subjects (98%) had AEs that were assessed by the investigator as related (possibly, probably, or definitely) to investigational product. The most frequent treatment-related AEs occurring in > 20% of subjects were hypoalbuminemia (69.4%), increased ALT (63.3%), increased AST (61.2%), peripheral edema (42.9%), pyrexia (42.9%), myalgia (40.8%), headache (36.7%), nausea (32.7%), fatigue (28.6%), edema (24.5%), hypotension (24.5%), and chills (22.4%). Treatment-related grade 3/4 AEs were reported in 30.0% of patients. Three deaths were reported (due to pneumonia, sepsis, and sepsis syndrome); none were considered treatment-related by the investigators. Treatment-related AEs that most frequently led to permanent discontinuation were hemolytic uremic syndrome (HUS), capillary leak syndrome (CLS), and blood creatinine increased, reported in 4 (5.0%), 2 (2.5%), and 2 (2.5%) patients, respectively. Seven patients (8.8%) had CLS (grade 2: n=5; grade 4: n=2), 7 patients (8.8%) had HUS (grade 2: n=2; grade 3: n=3; grade 4: n=2), and 4 patients (5.0%) had both CLS and HUS. In general, CLS and HUS events were manageable and reversible with appropriate supportive care, monitoring, and, in severe events, treatment discontinuation. Grade 3-4 AEs, regardless of attribution, occurring in at least 2.5% of patients included lymphopenia (20%), hypophosphatemia or anemia (10%), leukopenia

Version Date: 04/16/2025

(8.8%), hypertension, (7.5%), thrombocytopenia or neutropenia (6.3%), HUS, febrile neutropenia, or neutropenia (5%), and nausea, hypokalemia, hyponatremia, CLS, upper respiratory infection, hypoxia, lung infection, acute kidney injury, or erysipelas (2.5%). A number of eye changes have been reported in studies with moxetumomab pasudotox-tdfk; serious events including inflammation of the nerve for sight and retinal detachment have occurred in the acute lymphoblastic leukemia [14].

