- 1. End of treatment visit will occur 28-42 days after 1st dose of last cycle.
- All participants will be offered the opportunity to complete an NIH advance directives form (Section 12.3). This should be done preferably at baseline but can be done at any time during the study. The completion of the form is strongly recommended but not required.
- Within 4 weeks prior to enrollment, could be combined with pre cycle 1. Only anti-moxetumomab pasudotox-tdfk antibodies will be assessed.
- 4. CBC + Diff should be done every 3 months until 2.5y after EOT, then every 6 months.
-  Follow-up time points not requiring restaging are 1, 2 and 3.5 years after EOT, then every 2 years
- 6. Restaging requiring imaging, labs (and bone marrow if CR suspected) is 1.5 and 2.5 years after EOT, then every 2 years.
- Within 6 months of initiation of study therapy provided within 4 weeks after last therapy. Baseline HLA may be done anytime.
- PK and PK bioassay Time points: On days 1 and 5 of cycles 1,2,3,5,7. For cycles 1 and 2: pre, and immediately post, +/- 8 min, then 30+/-10, 60+/-15, 180+/-20,, and 360+/-50 minutes after moxetumomab pasudotox-tdfk end of infusion; On cycles 3, 5, and 7: pre and post infusion, 1-8 min; on cycles 4, 6, and 8 no PK will be drawn. Each ~6cc in K2EDTA tubes.
- 9. CT Neck-Pelvis is done at baseline to identify sites of disease, including spleen, and at EOT and restaging points MRI of these sites may be substituted. In asplenic participants without baseline sites of disease, MRI of the abdomen may be done at restaging time points. The entire neck to pelvis CT need not be repeated if the disease (splenomegaly) was contained within just the abdominal or abdominal-pelvis levels of the CT. Pre-cycle scans will only be performed if participant is being restaged.
- 10. Deviations on post-EOT time points may be +/- 2 months until 2.5 years and +/- 4 months thereafter.
- Chemistries includes sodium, potassium, chloride, bicarbonate, creatinine, glucose, blood urea nitrogen (BUN), albumin, calcium, magnesium, phosphorus, AST (SGPT), ALT (SGOT), total bilirubin, direct bilirubin, lactate dehydrogenase (LDH), total protein, alkaline phosphatase, creatine kinase (CK or CPK), and uric acid. Except on day 15. Day 15 only acute care panel along with CBC with c diff and urine analysis will be required.
- 12. Optional when not performed at NIH
- 13. +/-1 day,

Version Date: 04/16/2025

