#### **6.2** DATA ELEMENTS

## 6.2.1 Human Data Sharing Plan

- Documentation of dosage and timing of drug administration
- Outside laboratory, radiologic, and pathology results will be sent to the PI and entered into NCI C3D at NIH
- NIH labs and tests will be downloaded into C3D

Version Date: 04/16/2025

• A pre-existing (baseline) laboratory abnormality will be considered the last one obtained prior to the first dose of drug, unless the PI considers an abnormality of higher grade occurring within 100 days prior to the first dose to be a truer baseline.

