#### SAEs will be:

 Assessed for severity and relationship to study product and alternate etiology (if not related to study product) by a licensed study physician listed on the Form FDA 1572 as the site

Version Date: 04/16/2025

principal investigator or sub-investigator.

- Recorded on the appropriate SAE report form, the medical record and captured in the clinical database.
- Followed through resolution by a licensed study physician listed on the Form FDA 1572 as the site principal investigator or sub-investigator.

For timeframe of recording adverse events, please refer to Section 6.1. All serious adverse events recorded from the time of first investigational product administration must be reported to the sponsor.

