## 8.4.3.1 Reporting of Adverse Events (AEs) after the 30-day follow up period

At any time after a patient has completed the study therapy, if an Investigator learns of any SAE including sudden death of unknown cause, and he/she considers there is a reasonable possibility that the event is causally related to the investigational product, the investigator should notify AZ.

\* Investigative site must also indicate, either in the SAE report or the cover page, the **causality** of events **in relation to all study medications** and if the SAE is **related to disease progression**, as determined by the principal investigator.

Version Date: 04/16/2025

If patients who are gaining clinical benefit are allowed to continue study treatment post data cut off and/or post study completion, then all SAEs must continue to be collected and reported to Patient Safety within the usual timeframe.

Otherwise, after study treatment completion (i.e., after any scheduled post treatment follow-up period has ended) there is no obligation to actively report information on new AEs or SAEs occurring in former study patients. This includes new AEs/SAEs in patients still being followed up for survival but who have completed the post treatment follow up period (30 days).

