# 8.4.3.2 Reporting of Adverse events (AEs)

AEs for new primary malignant tumors reported during a study should generally be assessed as serious AEs. If no other seriousness criteria apply, the 'important medical event' criterion should be used. In certain situations, however, medical judgement on an individual event basis should be applied to clarify that the primary malignant tumor event should be assessed and reported as a non-serious AE. For example, if the tumor is included as medical history and progression occurs during the study, but the progression does not change treatment and/or prognosis of the malignant tumor, the AE may not fulfil the attributes for being assessed as serious, although reporting of the progression of the malignant tumor as an AE is valid and should occur. Also, some types of malignant tumors, which do not spread remotely after a routine treatment that does not require hospitalization, may be assessed as non-serious; examples include Stage I basal cell carcinoma and Stage IA1 cervical cancer removed via cone biopsy.

Non-serious adverse events and SAEs will be collected from the time consent is given, throughout the treatment period and up to and including the 30-day follow-up period. After withdrawal from treatment, subjects must be followed up for all existing and new AEs for 30 calendar days after the last dose of trial drug and/or until event resolution. All new AEs occurring during that period must be recorded (if SAEs, then they must be reported as indicated in Sections 8.3 and 8.4.1). All study-related toxicities/ SAEs must be followed until resolution, unless in the Investigator's opinion, the condition is unlikely to resolve due to the patient's underlying disease.

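### For about 4.5 to 5 of the six or more months of B-cell depletion after the last antibody dose, grade 3 or higher infections that are non-serious need not be recorded

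*Combined protocol and SAP*

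**What the plan says.** Section 6.1 has all adverse events documented from the first study intervention through end of treatment, and then: "After 30 days, only adverse events which are serious and related to the study intervention need to be recorded". It does not say what the 30 days are counted from. Section 8.2 makes 6.1 the governing rule: "For timeframe of recording adverse events, please refer to Section 6.1". Section 8.4.3.2 supplies an anchor: "subjects must be followed up for all existing and new AEs for 30 calendar days after the last dose of trial drug". Section 8.4.3.1 adds that, once the post-treatment follow-up has ended, "there is no obligation to actively report information on new AEs or SAEs occurring in former study patients".

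The Study Calendar (3.4) marks the adverse event row at baseline, pre-cycle and end of treatment (EOT). It has no mark at EOT+6 months, follow-up or restaging. Footnote 17 says adverse events are monitored at every visit. For the EOT visit itself, footnote 1 says: "End of treatment visit will occur 28-42 days after 1st dose of last cycle". Section 3.6 separately asks for a safety visit about 28 to 42 days after the last dose of study therapy.

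Blood counts continue after treatment ("CBC + Diff should be done every 3 months until 2.5y after EOT, then every 6 months"), and Section 6.2.1 brings them into the database: "NIH labs and tests will be downloaded into C3D". Under 6.1, an abnormal laboratory value becomes an adverse event only if it meets one of the listed conditions, such as symptoms, treatment or discontinuation.

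**The concern.** The primary objective (1.1.1) is the safety and toxicity of the combination, and Section 10.4.4 covers lesser toxicities as well as dose-limiting ones. The drug being added is an anti-CD20 antibody. Section 1.2.1 states that it clears normal B-cells from the circulation for at least six months after the last dose, and Section 14.2.2 describes late-onset neutropenia after rituximab. A delayed infection or neutropenia attributable to the antibody would be expected in those months, yet recording in most of them depends on the event being both serious and judged related.

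At stake is the description of late toxicity in a small single-arm trial. An absence of late grade 3 infections in the report could mean that none occurred, or that none had to be written down.

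**Working it through.** The plan states no figure here to reproduce. The check is a timeline, followed by a reading of the sections together.

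**Inputs**
- Antibody on day -2 of cycle 1 and on day 1 of cycles 2-8; moxetumomab on days 1, 3 and 5 (3.1, 3.1.1, 3.2.2). The schema has a day 0.
- Full recording ends 30 days after the last dose (8.4.3.2) or, at the latest, at the safety visit up to 42 days after the last dose (3.6).
- B-cell depletion of at least six months after the last antibody dose (1.2.1), taken as 183 days.
- Late-onset neutropenia: median duration 10 days, range 3 to 148 (14.2.2).

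**Days from last antibody to last moxetumomab**
- Last cycle is 2-8: day 1 to day 5 = 4 days.
- Cycle 1 only: day -2 to day 5 = 7 days.

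**Days after the last antibody covered by full recording, and what remains of 183**

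| Reading | Last cycle 2-8 | Cycle 1 only |
|---|---|---|
| 30 days after last dose | 4 + 30 = 34; 149 remain | 7 + 30 = 37; 146 remain |
| Latest safety visit | 4 + 42 = 46; 137 remain | 7 + 42 = 49; 134 remain |

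At 30.5 days per month, 134 to 149 days is 4.4 to 4.9 months. Full recording covers between 34/183 = 19% and 49/183 = 27% of the six months. The latest EOT visit (42 days after the first dose of the last cycle) falls between the two readings when the last cycle is 2-8: 183 − 42 = 141 days remain.

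**What is required in the remaining days**
- Serious and related: recorded (6.1), with supplier notification (8.4.3.1).
- Grade 3 or higher infection, non-serious: not required by any section, whatever the attribution.
- Serious, judged unrelated: the sections conflict. 6.1 does not require recording and 8.4.3.1 ends active reporting. 8.4.1.1 asks for all SAEs to go to the supplier regardless of causality and states no end date; 8.2 asks for all recorded SAEs to go to the sponsor but refers back to 6.1 for timing.
- Neutropenia: counts are in the database, but not as adverse events unless the laboratory-value rule is met.

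**How much the scheduled counts catch.** With counts 91 days apart and random onset, an episode of D days overlaps a scheduled count with probability min(1, D/91):
- 3 days: 3/91 = 3%
- 10 days: 10/91 = 11%
- 91 days or longer, including 148 days: 100%

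Counts prompted by symptoms would raise these figures. Blood counts say nothing about infections. Concomitant medications are marked at EOT+6 months and may show an antibiotic, but without an event term or grade.

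**The case against.** The best defence is that 6.1 sets a minimum. Investigators may record more, footnote 17 has adverse events monitored at every visit, and events that start inside the window are followed to resolution. This stands as far as it goes: the right description is not required to be recorded, rather than lost. But monitoring at a visit does not change what 6.1 obliges anyone to enter.

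A second defence is that 10.4.4 speaks of toxicities to an agent, so an infection judged unrelated lies outside what it promises. That is fair, and it makes non-serious infections that are related the clearest omission. In a single-arm trial of a disease that itself causes neutropenia and infection, however, attribution is a judgement best applied after the event has been recorded.

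A third is that late events without a comparator are hard to interpret. That is true and limits what the data can show, but recording response status with each event helps.

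Three stronger readings are tempting, and the documents do not support them.
- A reader might infer that full recording always stops 3 to 6 days short of the 40-day definition of late-onset neutropenia in 14.2.2 (40 − 37 and 40 − 34). That depends on the last-dose anchor in 8.4.3.2. If recording runs to a late EOT visit (day 42) or safety visit (day 46 or 49), the shortfall closes.
- A reader might cite the background statement "Three deaths were reported (due to pneumonia, sepsis, and sepsis syndrome); none were considered treatment-related by the investigators" as proof that attribution hides infections. Those deaths come from earlier moxetumomab trials, their timing is not given, and they were reported although judged unrelated.
- A reader might lean on the opportunistic-infection remark in 1.2.2 or on exclusion 2.1.2.9. The first concerns avoiding chemotherapy damage; the second concerns HIV-positive participants who do not meet its treatment and CD4 conditions. Neither shows a late infection risk from this regimen.

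A looser reading also favours the plan. Counting 30 days from the latest EOT visit, which no section states, gives 42 + 30 = 72 days when the last cycle is 2-8 and still leaves 183 − 72 = 111 days.

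**Conclusion.** The point holds, as a minor one. After the end of full recording, roughly 4.5 to 5 of the at least six months of B-cell depletion carry no requirement to record non-serious grade 3 or higher infections, and the sections disagree on serious infections judged unrelated. Late neutropenia is partly recoverable from scheduled counts, which miss most short episodes.

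The length of the gap rests on taking six months as 183 days and on full recording ending between 30 days after the last dose and the latest safety visit. The six-month figure is given for rituximab and is assumed here for Ruxience. These are calendar shares, not counts of harm: the documents give no rate of late infection or neutropenia and no share of grade 3 infections that would be non-serious, so the number of missed events cannot be stated.

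The effect is confined to the description of late toxicity. The limit of 2 dose-limiting toxicities in 10 participants (10.4.2) is untouched, because the window in 3.1.2 also closes 30 days after the last moxetumomab dose. The MRD-free CR comparison does not use these data.

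**What to change.** In 6.1, replace the sentence with: *After 30 days from the last dose of study drug, only adverse events that are serious and related need to be recorded, except that grade 3 or higher infections and neutropenia are recorded regardless of seriousness or attribution through the EOT+6-month visit or the start of alternative HCL therapy, whichever is first.* State that for neutropenia this exception also overrides the laboratory-value rule in 6.1; otherwise that rule would screen out asymptomatic episodes.

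In the Study Calendar, mark the adverse event row at EOT+6 months.

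In 10.4.4, report the number and proportion of participants with these late events, with response status at the time, supplemented by grade 3-4 neutrophil counts from post-EOT blood counts already in the database. Note that counts every three months miss most short episodes, so finding none is not evidence of absence. For participants already past that visit, take the events from its records and label them retrospective and possibly incomplete.

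The cost is small: text in two sections, one calendar mark and a few extra entries. Blood counts and concomitant medications are already scheduled at that visit, so no new visit, test or staff is needed. The downside is that some entries will reflect relapsing HCL, and some will need records from outside NIH.
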